1. Baduanjin qigong is more effective than no-intervention control in (i)reducing cancer-related symptoms and symptom distress, (ii)improving mental health, (iii)enhancing quality of life, (iv)positively altering biomarkers, (v)enhancing mindfulness level.

- 2. Mindfulness meditation is more effective than no-intervention control in similar areas and directionality as the above (i) to (v).
- 3. There would be commonalities and differences between Baduanjin qigong and Mindfulness meditation in a)type of outcome variables, b)magnitude of change, c)time when significant outcomes emerge, d)frequency and length of self-practice and long-term compliance.
- 4. The associations among physical and psychological variables as well as psychophysiological biomarkers and the changes of such associations across the time points are exploratory.

Research Plan and Methodology

Research design

This study will utilize a 3-arm randomized controlled trial design with waitlist control. A conceptual model is provided in Appendix A. Upon recruitment, participants will be screened according to the inclusion and exclusion criteria (Appendix B). Baseline data will then be collected. Subsequently, eligible participants will be randomly assigned into one of the 8-week (i)Baduanjin qigong group, (ii)Mindfulness meditation group, and (iii)Waitlist Control group. The Waitlist Control group will continue to receive routine medical care and will have the option to attend either of the interventions after the study is completed. Participants from all 3 arms will be assessed on 4 time points (i)baseline prior randomization, (ii)mid-intervention (4th week), (iii)post intervention (8th week), (iii)6 months post-intervention. Participants will complete the study in 8 months.

Sample size determination, Participant eligibility and Recruitment

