(b) *The Mindfulness meditation Intervention* which has been used by co-Is ([name] and [name]) in previous studies is developed based on the core components of the established Mindfulness-Based Stress Reduction and the Mindful Self-Compassion program with adaptation for local practice[57, 62]. The focus of the group is to nurture mindful awareness, acceptance, and self-compassion. The group sessions are composed of a combination of mindfulness-based practice, relaxation, and yoga exercise (Appendix D). The basic philosophy of this intervention is the emphasis of the nurturing of self-kindness attitude, and non-attachment attitude towards inter-personal connectedness and letting go of self-criticism, need for control, and defensive separation in times of adversity. Short breaks will be arranged between each practice. Adjuvant to the in-session practices, participants are recommended to practice the mindful techniques every day for at least 20 minutes while keeping a record of their practice.

(c) Waitlist control group members will continue with routine care and can join either the Baduanjin or Mindful intervention after the 6-month post-intervention assessment.

Ethics

This study will be reviewed by the HKU/HA Institutional Review Board. Written informed consent will be obtained from all participants. To ensure confidentiality, codes will be used to replace names. All data collected will be kept in locked spaces and destroyed 3 years after the study ends. The study will also be registered with the Hong Kong clinical trial registry.

Measurements

Assessments pertain to areas of (i)cancer-related symptoms and symptom distress, (ii)mental health, (iii)quality of life, (iv)biomarkers, (v)mindfulness, (vi)compliance, and (vii)demographic and clinical details. Self-rated scales and salivary cortisol are administered by participants themselves while blood pressure would be measured by the trained research assistant blinded to the randomization. Measurements are taken at all time points except demographic and clinical details.

Cancer-related symptom, symptom distress and quality of life

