- (f) Salivary cortisol. Salivary cortisol collection will be conducted by participants themselves. Saliva samples will be collected at 5 prescribed times (awakening, 45 minutes postawakening, 12:00pm, 5:00pm and 9:00pm) using the collection device, Salivette, which includes a cotton swab to place under the tongue. Smoking, eating and drinking should be avoided and refrained one hour prior to saliva collection. Samples collected will be kept frozen at -20°C.Daily condition measures with salivary cortisol-Measures on participants' health behaviors and activities on the day of saliva collection will be collected along with cortisol. These include (i)sleep quantity that day (hours of sleep at night and nap hours), (ii)subjective sleep quality rated on a scale of 1-10, (iii)smoking habit and the number of cigarettes that day (iv)alcohol/coffee drinking habit and the approximate amount that day, and (v)subjective evaluation of stress levels on the day of collection rated on a scale of 1-10. All the above measures will affect the diurnal cortisol rhythm and must be considered in analysis.
- (g) Blood pressure and heart rate. Following recommended procedures by the Canadian Medical Association[69], blood pressure and heart rates would be measured twice from each arm with a five minute rest intervals between measurements. The four collected readings will be averaged.
- (h) Mindfulness. The Chinese Five Facet Mindfulness Questionnaire (Short form) will be used upon permission. It has 5 domains, observing, describing, acting with awareness, nonjudging to inner experience and nonreacting to inner experience[70]. The 5-point Likert scale has 20 items.

- (i) Compliance. Participants will record their daily duration of qigong or mindfulness meditation practice over the course of the study. This will provide information on the frequency and intensity of practice, and maintenance of self-practice habits after the intervention period.
- (j) Demographics. Participants socio-demographic, such as age, gender, education level, employment status and marital status, as well as clinical profile, including cancer diagnosis, staging, treatment and medication record, onset of mood disturbances if any, critical events around the time of onset, physical exercise habits, complementary treatment used, and psychosocial support service utilization, will be documented based on self-report.

Data analyses

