Employing baseline data from both the experimental and control groups, correlation analyses will be used to understand the relationship between the parameters reflected on the mind and body which include diurnal cortisol patterns, subjective stress and assessments on the psychological symptoms, sleep patterns, health-related quality of life. Changes of those associations across time can be analyzed by latent growth modeling using Mplus.

4. Analysis of salivary cortisol data (for all objectives and hypotheses)

Saliva samples will be centrifuged at 3000rpm for 15 minutes at room temperature. Cortisol levels will be determined with an enzyme-linked immunoabsorbent assay kit (EIA, Salimetrics, Inc) in the HKU Clinical Oncology Lab. The assay sensitivity is 0.193 nmol/l and the intra-assay and inter-assay coefficients of variation are 3% and 10% respectively. Due to the skewed distribution of salivary cortisol data, natural logarithm will be used to transform the raw cortisol data to yield an unskewed distribution for analysis. The mean cortisol level will average the 5 collected across the day and total cortisol level is measured by the area under the curve.

To explore individual trajectories of changes in cortisol level over time and also the complex relationships between different variables, a two-level individual growth curve model using Mplus software will be adopted as cortisol measures at 5 daily time points are nested within participants. This method is a variant of multiple regression modeling appropriate for the nested structure of our data.

Reference

1.Hong Kong Cancer Registry. Colorectal Cancer in 2011. Nov, 2013; Available from: http://www3.ha.org.hk/cancereg/colorectum_2011.pdf.

2.Cotrim, H. and G. Pereira, Impact of colorectal cancer on patient and family: implications for care. European Journal of Oncology Nursing, 2008. 12(3): p. 217-226.

3.Flynn, K.E., et al., Sleep-wake functioning along the cancer continuum: focus group results from the Patient-Reported Outcomes Measurement Information System (PROMIS®). Psycho-Oncology, 2010. 19(10): p. 1086-1093.

4.Jonsson, C.A., A. Stenberg, and G.H. Frisman, The lived experience of the early postoperative period after colorectal cancer surgery. European journal of cancer care, 2011. 20(2): p. 248-256. 5.Lavdaniti,M.,etal.,Evaluation of depression in colon cancer patients. HealSci

Journal,2012.6:p.681-92.

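### The two-level cortisol model has no place for the four assessments, so no planned analysis estimates an arm effect on change in diurnal rhythm

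*Combined protocol and SAP*

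**What the plan says.** Research design: "Participants from all 3 arms will be assessed on 4 time points" (baseline, week 4, week 8 and 6 months after the intervention). Measurements: "Measurements are taken at all time points except demographic and clinical details", so salivary cortisol is collected at all four. Biomarkers (f) sets 5 saliva samples on a collection day, from awakening to 9:00pm. It also records that day's sleep, smoking, alcohol or coffee intake and stress, and adds: "All the above measures will affect the diurnal cortisol rhythm and must be considered in analysis".

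The heading of Data analyses item 4 applies the cortisol analysis to every objective and hypothesis. The item defines two daily summaries, the mean of the 5 samples and the area under the curve. It then gives one model for the individual samples. Its aim is stated as "To explore individual trajectories of changes in cortisol level over time". Its form is a growth curve model with two levels, fitted in Mplus and chosen because "cortisol measures at 5 daily time points are nested within participants". The plan describes this as suited to the nesting in the data.

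Data analyses item 1 separately plans latent growth models over the four assessments, comparing each intervention with waitlist, and says that all models use robust maximum likelihood. Item 2 compares the linear slopes of the two interventions.

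**The concern.** The only model that can represent the shape of the day has one stated time axis, the 5 daily samples, and one stated cluster, the participant. The other time axis, the four assessments over which the interventions act, is not mentioned, and neither is the collection day as a unit. The growth models of item 1 do cover the assessments, but they need one value per assessment. The two summaries on offer describe how much cortisol there is over the day, not how it falls: two participants can share a mean and an area and have different diurnal slopes.

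This matters because rhythm is the reason for collecting cortisol. Theoretical contributions speaks of effects on circadian cortisol rhythm, and the section on diurnal cortisol and cancer ties its distortion to tumour characteristics and survival. Biomarkers belong to primary objective 1 and pace of change to primary objective 2. If the text is followed, the rhythm question goes unanswered. If it is repaired during analysis, the form of the repair is chosen with the data in hand.

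**Working it through.** The plan gives no figure for the cortisol model, so there is none to reproduce.

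**Structure.** 4 assessments × 5 samples = up to 20 samples per participant. Within a participant there are 19 degrees of freedom: 3 between days and 16 within days.

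**What the model can estimate.** With arm and a linear time of day only, the fixed effects are 3 arms × (intercept, slope) = 6 parameters, none of which is an arm effect on change. With assessment added, there are 3 × 4 × 2 = 24 parameters. The design matrix then has rank 24, so the effect can be estimated once it is written down.

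**Pooling without an assessment term.** Take complete data, equal weight per assessment and no arm difference at baseline. A slope effect δ at all three later assessments appears as (0 + δ + δ + δ)/4 = 0.75δ. One at the last two appears as (0 + 0 + δ + δ)/4 = 0.50δ.

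**Assessment added, no day-level random effect.** Set the within-person variance to 1, with a share ρ shared by all samples of a day and 1 − ρ left over. The documents give no ρ, so 0.1 to 0.3 is assumed. Fit a participant intercept only.

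- Mean square governing change in level: 5ρ + (1 − ρ) = 1 + 4ρ.
- Mean square governing change in diurnal slope: 1 − ρ.
- Mean square the model uses for both: [3(1 + 4ρ) + 16(1 − ρ)]/19 = 1 − 4ρ/19.

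True/model standard error is the square root of the ratio. At ρ = 0.2, level is √(1.8/0.958) = 1.37 and slope is √(0.8/0.958) = 0.91. Type I error is 2[1 − Φ(1.96/ratio)], two-sided at a nominal 5%.

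| ρ (assumed) | Level: true/model SE | Type I error | Slope: true/model SE | Type I error |
|---|---|---|---|---|
| 0.1 | 1.20 | 10.1% | 0.96 | 4.1% |
| 0.2 | 1.37 | 15.3% | 0.91 | 3.2% |
| 0.3 | 1.53 | 20.1% | 0.86 | 2.3% |

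**If the slope also varies between days.** Let the residual variance be 1, A = 5 × variance of the day intercept and B = Sxx × variance of the day slope, where Sxx is the sum of squares of the sampling times. With a participant intercept and slope fitted, the model uses 1 + (A + B)/6, while the correct value for slope change is 1 + B. The model's standard error is too small only if 1 + B > 1 + (A + B)/6, that is, B > A/5. At ρ = 0.2, A = 5 × 0.25 = 1.25, so the threshold is B = 0.25. Model/true SE is then 1.10 for B = 0, √(1.375/2) = 0.83 for B = 1, and √(1.542/3) = 0.72 for B = 2.

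**Robust standard errors.** A simulation (42 per arm, that is 126/3; 4000 runs per scenario; waking at 07:00 assumed) compared model-based errors with sandwich errors clustered on participant. For change in level at ρ = 0.2 with B = 0, the empirical SE was 0.207, the model-based SE 0.152 and the robust SE 0.204. Robust type I error was 0.05 to 0.06 in every scenario.

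**Variance components.** Robust errors leave these as they are. In the participant-intercept fit the residual becomes 1 − 4ρ/19, and the remaining 4ρ/19 is credited to stable differences between participants: 4 × 0.2/19 = 0.042 at ρ = 0.2.

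**The case against.** The strongest reply is that this is a gap in wording. Several parts of it stand.

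- A reader might infer that the arm effect on change in rhythm is not identified. It is: the data support it, and even a two-level model estimates it once assessment terms are added. It is unspecified.
- Change in the cortisol mean or area has a route through the growth models of item 1, where one value per day removes the nesting problem.
- Robust maximum likelihood is stated for all models. If it is clustered on participant, it largely protects the fixed-effect standard errors. The sentence sits under item 1, so its reach to item 4 is the natural reading but is not spelled out.
- Study Hypotheses speaks of positively altering biomarkers, not of rhythm. Rhythm comes from the rationale.
- The same-day measures, if entered, would absorb some day-level variance. The model does not say at what level they enter.
- Fitted separately at each assessment, a two-level model matches the data of that one day, and an added arm term would compare rhythm between arms on it. The plan states neither step, and separate fits give no test of change or of its pace.

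None of this supplies the missing term. Robust errors cannot protect an effect that the model does not contain.

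**Conclusion.** The concern holds as a mismatch between the stated model and the data. Followed as written, the plan estimates no arm effect on change in diurnal rhythm. This should be corrected, since the plan presents the two-level structure as fitting its data and the section serves every objective.

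The dilution factors of 0.75 and 0.50 apply only if assessments are pooled with no assessment term, and rest on equal weights and no baseline difference. The standard-error figures apply only to a different variant, with assessment added, no day-level random effect and model-based errors. The two harms are alternatives, because an effect absent from the model has no standard error. All the error figures rest on an assumed ρ and balanced data.

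Two stronger readings are not supported. A reader might infer inflated type I error for the rhythm test. The 10.1% to 20.1% belongs to change in level; with day-to-day variation in level only, the rhythm test is conservative, and it becomes liberal only if B > A/5. A reader might also infer that the individual trajectories would be mostly day-to-day noise. That needs a random slope over assessments, which the plan does not state, and a true slope variance of zero, which is an assumption. What stands is that the variance components are not protected by robust errors.

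**What to change.** Replace the two-level model in Data analyses item 4 with sample within assessment day within participant. Three levels will do, or the four assessments modelled jointly in a multivariate two-level model. Specify:

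- random effects for participant and for participant-by-assessment;
- fixed effects for time of day, assessment, arm and their interactions;
- the daily condition measures from Biomarkers (f), entered at day level;
- the arm by assessment by time-of-day slope term as the rhythm estimand;
- that robust standard errors clustered on participant apply to this model.

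State also that the mean and area go into the growth models of items 1 and 2, if that is the intention. The cost is wording and modest extra modelling, with no new data and no change in sample size. Some standard errors may widen.

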Appendix A: Conceptual model of the proposed study

Appendix B: Inclusion and exclusion criteria

Inclusion Criteria	Exclusion Criteria
 Diagnosis of primary colorectal cancer of any stages 0 to III An expected survival length of 12 months or longer 0.5 to 5 years following completion of main treatment for colorectal cancer Ages 18 or higher Chinese speaking 	 Regularly practicing baduanjin qigong, other forms of qigong, taichi, meditation, mindfulness practices or yoga once a week or more Having participated in the above trainings in the past 6 months Severe cachexia, dizziness, bone pain, nausea or significant orthopedic problem or other contraindications for mild to moderate physical exertion Diagnosis of major medical or psychiatric disorder besides cancer (including but not limited to severe cardiovascular disease, epilepsy, uncontrolled diabetes, untreated hypothyroidism, delirium or dementia) Recurrence of colorectal cancer or other cancers

Appendix D: Main components of the Mindfulness Meditation Program

- 1. Introduction to Mindfulness
- 2. Practising mindfulness meditation
- 3. Practising loving-kindness meditation
- 4. Developing self-love through mindfulness meditation
- 5. Exploring meaning in life through mindfulness application
- **6.** Bringing in difficult emotions
- 7. Practising self-kindness and gratitude as way of coping wrong difficult emotions and difficult situations in life
- 8. Transferring mindfulness meditation as a way of living
